Following completion of the screening visit, applicants will be required to complete food records for one week. Applicants will be provided with booklets or assisted in downloading a free mobile app to monitor their food intake over the course of the week. Applicants must return their completed food records (via mail or email) before being provisionally accepted into the study. Participants will be officially accepted into the study and randomized during a subsequent randomization visit that will occur within one month of beginning the study intervention.

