6.2 Study Visits

Screening visit. The following procedures will be completed at the screening visit as discussed above: informed consent, medical history, weight, height, and meeting with psychologist whose assessment will be used as a part of determining the subject's eligibility for the study. This medical history will be reviewed by the study physician or nurse practitioner to determine whether there are any contraindications to weight loss. These contraindications include but are not limited to: any major active kidney, liver, cardiovascular, or cerebrovascular disease; type 2 diabetes; or the use of any medications that significantly affect weight (weight loss or weight gain, including steroids). Female participants will be ineligible for the study if they are pregnant or nursing. Applicants with a history of cardiac events or other significant CVD risk factors may also be asked to supply a letter from their primary care physician providing medical clearance for them to participate in this study. Applicants will be required to monitor their food intake following the screening visit and return their food records before being provisionally accepted into the study.

Randomization visit. Within one month of the start of the group intervention, participants will attend a visit in which their weight and blood pressure will be measured and, if they still meet all study criteria, they will be randomized to their treatment group. Accelerometers will be given to participants to monitor their activity for 7-10 days. Participants will return their accelerometers in person, at which time their activity for the past week will be assessed with a structured interview. Participants may be held financially responsible if the accelerometer is lost, stolen, or not returned.

If a participant is randomized but no longer able to attend groups as scheduled, it may be available to them to begin the group intervention, in the same treatment condition as assigned at randomization, in a subsequent cohort. In this case, baseline measurements will be repeated within one month of the start of treatment.

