BWL intervention. Participants in this group will be provided with 20 weekly BWL sessions, based on the Diabetes Prevention Program (DPP) manual,⁵⁹ followed by 6 monthly weight loss maintenance sessions and 3 every-other-month sessions (for a total of 29 visits over 72 weeks). A diet of 1200-1499 calories per day will be prescribed for participants < 250 lb, and 1500-1800 for those ≥ 250 lb.^{59,60} Participants will be instructed to eat a balanced deficit diet with approximately 15-20% of kcal from protein, 20-35% from fat (less than 10% from saturated fat), and the remainder from carbohydrates.⁵⁹ Session topics during the first 20 weeks will include self-monitoring, stimulus control, slowing eating, social support, cognitive restructuring, portion sizes, and goal-setting.⁵⁹ Those during weeks 21-72 will focus on continued self-monitoring and skills required for weight loss maintenance and relapse prevention. BWL sessions will last 90 minutes. Beginning at week 5, 60 minutes of the group session will be devoted to BWL content, with an additional 30 minutes devoted to discussing recipes and food preparation.

Physical activity will be prescribed at a level consistent with data showing that ≥ 250 min/wk is associated with improved long-term weight loss.^{12-14,61} Activity will begin at week 2 with 60 min/wk, and will gradually progress by 10 minutes over 2-4 week intervals until achieving 150 min/wk by week 20, 200 min/wk by week 46, and 250 min/wk by week 72. Participants will be instructed to spread the 150-250 minute doses of activity equally across at least 5 days, and to accumulate their structured physical activity in bouts that are ≥ 10 minutes in duration. Moderate intensity will be prescribed with an emphasis on walking; the vast majority of our research participants self-select this form of activity.

Participants who cannot attend any given group session will be offered a brief (10-20 minute) make-up session (in person or by phone) during the week with the group leader or a study staff member. Participants may also meet briefly with the group leader individually, outside of group sessions, up to 3 times during the initial 20-week study period if they have not lost at least 1% of their body weight by week 4, report difficulty controlling their eating, or describe other challenges preventing them from adhering to the program that cannot be fully covered during group sessions.

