Participants will be expected to attend 4 assessment visits throughout the course of the study: at baseline, week 20, week 46, and week 72 (or within 4 weeks of each assessment period). Three of these assessment visits (baseline, week 20, and week 72) will include a fasting blood test, which will include a comprehensive metabolic panel (CMP), lipid panel, insulin, high sensitivity C-reactive protein (hs-CRP), and hemoglobin A_{1c}. These tests will require approximately 34 mls of blood. Blood pressure, pulse, and waist measurement will also be measured at these outcome assessment visits, and weight will be measured at all assessment visits.

Participants will also be asked to monitor their physical activity and complete questionnaires at baseline, week 20, week 46, and week 72. Questionnaires will be completed online or administered/returned via mail or at scheduled group sessions. Accelerometers will be administered at scheduled group sessions or assessment visits and returned in person or by mail, with an accompanying brief interview to assess activity over the past week (in person or by phone).

Adjustments to outcome assessment visits due to COVID-19. During the pandemic, in-person assessment visits will be replaced with remote assessments whenever possible. Specifically, all week 46 assessment visits will be conducted remotely for the duration of the pandemic. If permitted by the city, institution, and funding sponsor, week 20 and week 72 assessment visits will be offered in-person, in order to allow for the measurement of blood pressure and a fasting blood test. All local and institutional safety regulations will be followed when conducting in-person visits. Participants with safety concerns or other barriers that prevent them from attending in-person assessment visits will be offered remote assessments without penalty.

Remote assessment visits will be scheduled during the morning and will involve a brief phone call with the study coordinator, measurement of weight (and for weeks 20 and 72, measurement of waist circumference), monitoring of activity with an accelerometer device, and completion of online questionnaires. As described above, all participants will be sent an EatSmart Precision Digital Scale (with a tape measure included in the package). For remote assessments, participants will be asked to use the EatSmart scale to weigh themselves in duplicate, in kilograms, in the morning before eating anything. Participants will be asked to send

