6.3 Outcome Measures

Primary outcome. Percent weight loss from baseline to week 72 is the study's primary outcome. At week 72, participants in the stigma + BWL intervention are predicted to maintain their 9% reduction in initial weight, as compared to a significantly smaller 5% reduction in the BWL alone group. Duplicate measures of height (with a wall-mounted stadiometer; Veeder-Root, Elizabethtown, NC) will be obtained at screening, and weight (with a digital scale; Detecto, model 6800A) will be measured at screening, randomization (baseline), and at weeks 20, 46, and 72. Weight will also be measured at all group sessions. Percent weight loss from baseline to weeks 20 and week 46 will be assessed as secondary outcomes, along with categorical weight loss at weeks 72, 46, and 20 (loss of $\geq 5\%$ and $\geq 10\%$ of initial body weight at each time point). Participants in the BWL group are predicted to lose 8% of their initial weight at week 20. Participants in the stigma + BWL group are expected to lose 1% more of their initial weight (9%) at week 20 due to greater engagement in physical activity.

Secondary outcomes.

Physical activity. All participants will be given triaxial accelerometers (ActiGraph GT9X) to wear on their wrist for a 1-week period within 4 weeks of each assessment period (baseline and weeks 20, 46, and 72). Accelerometry has been used in numerous clinical trials,⁶²⁻⁶⁵ and the ActiGraph to be used in this study was adopted in the 5-year extension of the Look AHEAD study. Established activity counts will be used to identify thresholds of physical activity (sedentary, light, moderate, vigorous).⁶⁶ Self-reported physical activity will be assessed with the Paffenbarger Physical Activity Questionnaire⁶⁷ to obtain specific information on the types of activity participants engage in, and a brief questionnaire used in prior studies⁶⁸ to collect data on sedentary behavior. Self-efficacy will be assessed with the Self-Efficacy for Exercise Scale⁶⁹ Exercise Outcome Expectations and Barriers Scale (perceived barrier items only),⁷⁰ and Weight and

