All data will be analyzed with a modified intention-to-treat principle. Participants who attend at least one group meeting (i.e., receive a dose of treatment) will be included in the analyses; participants who do not attend a single group meeting will not be included in the analyses. Analyses will be two-tailed with a significance level of 0.05, and will be conducted using SPSS version 24.0 or SAS version 9.4. To assess the primary outcome of percent weight change by treatment group, a mixed effects model will be fit with Treatment Group (*stigma+BWL, BWL*) as a between subjects factor and Time (*Weeks 20, 46, 72*) as a categorical within-subjects factor. We will use the group x time interactions with the time main effect to estimate and test treatment group differences at each time point, with the 72-week time point as our primary test. In fitting a mixed effects model with residual maximum likelihood (REML), a variance-covariance structure must be selected. The criteria for selecting the best form of the variance-covariance structure will be based on criteria such as the Akaike's Information Criterion (AIC). We will include as baseline covariates any variables that differ significantly between the treatment groups at baseline and show significant relationships with the outcome. The results from the mixed model will be summarized by mean(SE) for each treatment group at each time point. Residual analyses will be conducted to check for outliers and influential points and violations in the normality assumption. If violations are detected, variance-stabilizing transformations will be considered. Logistic regression will be used to test for between-group differences in categorical weight loss ($\geq 5\%$ and $\geq 10\%$ of initial body weight) at weeks 72, 46, and 20.

The second aim of assessing changes in physical activity and self-efficacy, and the secondary aims of comparing changes in cardiometabolic risk factors and psychological well-being (including WBI), will be analyzed using the same methods as described above for the mixed effects model used for the primary aim. Changes in all outcomes will be summarized by mean(SE) for each treatment group at each time point. Logistic regression will be used to test for between-group

differences at weeks 20, 46, and 72 in the percentage of participants who have remitted from elevated WBI, as indicated by no longer having a score of 4 or above.

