This study will consider death, pregnancy, bariatric surgery, amputation, and other major medical events or procedures that require a participant to terminate treatment as "censoring events." For primary analyses, participants experiencing these events will be censored at the last measured weight before the event occurred. As discussed above, the primary analysis techniques being employed (i.e., linear mixed models) can accommodate incomplete participant response profiles, so these participants will still be included in the analyses. Additional sensitivity analyses may be conducted in which data will be censored due to other factors that directly affect weight (e.g., change of medication that affects weight, receipt of additional weight-related treatment, change in smoking status, or other major medical changes that occur within 3 months of an assessment visit).

Additional analyses may be conducted to explore potential effects of cohort, time of group meeting, and group leader on weight loss and changes in WBI. Analyses may also explore potential differences in attendance between groups and the effects of attendance on weight loss and changes in WBI.

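### Randomized participants who attend no group meeting are left out of every analysis, and the plan has neither an all-randomized analysis nor a count of non-starters by arm to show what this does to the week-72 contrast

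*Combined protocol and SAP*

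**What the plan says.** The analysis plan in section 7 sets one population for all data. The inclusion half reads "Participants who attend at least one group meeting (i.e., receive a dose of treatment) will be included in the analyses"; the exclusion half reads "participants who do not attend a single group meeting will not be included in the analyses".

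Four other parts of the protocol bear on this:

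- **Timing.** Section 6.1 has participants "randomized during a subsequent randomization visit that will occur within one month of beginning the study intervention". Section 6.2 foresees the problem ("If a participant is randomized but no longer able to attend groups as scheduled") and says that such a person may be able to join a later cohort in the same arm, with baseline measured again.
- **Make-up sessions.** Section 6.2, under the BWL intervention, states: "Participants who cannot attend any given group session will be offered a brief (10-20 minute) make-up session (in person or by phone"). The stigma + BWL arm has the same provision.
- **Weights.** Section 6.3 says weight "will be measured at screening, randomization (baseline), and at weeks 20, 46, and 72". Section 6.2 says "Participants will be expected to attend 4 assessment visits throughout the course of the study" and does not make those visits depend on group attendance.
- **Other analyses.** The sensitivity analyses in section 7 are optional and censor further data. The remaining optional analyses cover attendance and "potential effects of cohort, time of group meeting, and group leader on weight loss" and on changes in weight bias internalization. None brings the excluded participants back.

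**The concern.** Randomization protects a comparison of the groups as randomized. Once people are removed for something that happens afterwards, here never attending a group, the comparison is between starters in one arm and starters in the other. If the proportion who never start differs by arm, and non-starters would have lost less weight, the contrast moves without any treatment effect.

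Two features of the plan leave room for this. First, the arms receive different session content and meeting time is treated as something that can vary. The documents do not say whether meeting times are matched across arms or when participants learn their assignment. Second, the rule equates group attendance with receiving treatment, while make-up sessions take place outside the group. Read literally, someone who had only make-up sessions was treated and is still excluded.

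Percent weight loss at week 72 is the only outcome for which the trial is powered. A reader of the results would want to see that the exclusion did not matter, and the plan does not produce the figures to show it.

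**Working it through.** **Inputs from section 7:** means of 9% and 5% at week 72, SD 7, 52 per arm, 20% attrition, ICC 0.80, 4 assessments, two-sided alpha 0.05. **Assumed, because the documents give no figures:** the proportion who never start in each arm, their prognosis, and their weight change.

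**1. Reproduce the plan.** Variance of the four-visit mean: 49 × (1 + 3 × 0.8)/4 = 41.65. This requires 41 evaluable per arm; 41/0.8 rounds up to 52, or 104 in total, as stated. With 52 × 0.8 = 41.6 per arm, SE = √(2 × 41.65/41.6) = 1.415 and power = Φ(4/1.415 − 1.96) = 80.7%. The sample size has no error on this basis. For a single visit, SE = 7 × √(2/41.6) = 1.53. Both are used below.

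**2. Selection when there is no true difference.** Let p₁ and p₀ be the proportions excluded, and d how far non-starters fall below the mean of their whole arm. The starters' mean then exceeds the arm mean by d × p/(1 − p), so the contrast shifts by d × [p₁/(1 − p₁) − p₀/(1 − p₀)]. With d = 3.5 to 7 (0.5 to 1 SD):

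| Never start | Shift, points | Type I error, SE 1.53 | Type I error, SE 1.415 |
|---|---|---|---|
| 5% and 5% | 0 | 5.0% | 5.0% |
| 6% and 2% | 0.15 to 0.30 | 5.1% to 5.5% | 5.1% to 5.5% |
| 10% and 4% | 0.24 to 0.49 | 5.3% to 6.2% | 5.3% to 6.4% |

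For example, 10% and 4% with d = 7 gives 7 × (0.1111 − 0.0417) = 0.49, which is 0.32 of the larger SE and 0.34 of the smaller. The sign reverses if the arms swap. In people, 6% and 2% of 52 is about 3 and 1; 10% and 4% is about 5 and 2.

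A lopsided case marks the outer edge. Suppose all non-starters are in one arm, they lose 0%, and both arms as randomized lose 5%. Five non-starters give 5 × 52/47 − 5 = 0.53 points and a rejection rate of about 6.6%; ten give 5 × 52/42 − 5 = 1.19 points and about 12.5%.

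**3. Change of estimand.** If the planned effects hold among starters and non-starters lose 0%, the all-randomized difference is:

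- 5% in each arm: 0.95 × 9 − 0.95 × 5 = 3.80
- 10% in stigma + BWL, 4% in BWL: 0.90 × 9 − 0.96 × 5 = 3.30
- the reverse: 0.96 × 9 − 0.90 × 5 = 4.14

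These differ from 4.0 because they answer a different question. They do not measure bias.

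**4. Power with 5% non-starters in each arm.**

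- Current rule, non-starters lost on top of the 20% attrition: n = 52 × 0.95 × 0.8 = 39.5, SE = 1.452, power = 78.7%.
- All randomized, non-starters at 0%, SE held at 1.415: Φ(3.80/1.415 − 1.96) = 76.6%.

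**The case against.** The rule is disclosed, prespecified and objective, and modified populations of this kind are common. Three features limit harm. Content is identical in both arms until week 5, so someone who attends nothing has not reacted to arm-specific material. Applicants must return a week of food records before provisional acceptance and are re-checked against the criteria at randomization, which screens out the poorly committed. Deferral to a later cohort may rescue some who cannot start on time. All of this stands. It makes differential non-starting less likely without excluding it, since schedule or knowledge of assignment can act before the first session.

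The documents do not support four stronger readings that a reader might infer:

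- *The primary result is biased.* No non-starting rates are given, and nothing states that meeting times differ by arm. Meeting time is only listed beside cohort and group leader as something to explore.
- *The effect could never be checked.* Baseline weight exists for everyone randomized, baseline characteristics are compared by randomized group, and attendance may be explored. An unplanned check would be feasible; the gap is in the plan as written.
- *Virtual or telephone attendance is undefined.* The COVID-19 paragraph in section 6.2 already treats virtual meetings as group sessions that members may join by phone. Only make-up sessions are unclear, and a participant with nothing but make-ups would be rare.
- *Renaming the population is enough.* A participant with no post-baseline weight adds nothing to a mixed model of percent change at weeks 20, 46 and 72, so a stated assumption is also needed.

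**Conclusion.** The concern holds in limited form. The stated rule yields a primary contrast that is not between the groups as randomized, and the plan would not show whether that matters. On assumed rates the effect is small: nothing when non-starting is equal, 0.15 to 0.30 points at 6% and 2%, and 0.24 to 0.49 points at 10% and 4% with type I error of about 5.3% to 6.4%. It becomes large only if many non-starters fall in one arm and almost none in the other, which nothing in the documents suggests. The magnitudes rest entirely on assumed counts and prognosis. The exclusion and the missing all-randomized analysis rest on the text itself. This is a worthwhile, inexpensive improvement and does not show that the trial's conclusion would be wrong.

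**What to change.** 1. Add a prespecified analysis of the primary outcome in all randomized participants, as assigned. Preferably make it primary, with the modified population beside it; at minimum, make it a named sensitivity analysis.
2. State that the week 20, 46 and 72 weights are sought from everyone randomized, whether or not they attend groups. This is mostly clarification, since the assessment visits are not tied to attendance.
3. Include participants with no post-baseline weight through a stated assumption, such as 0% loss. Use the randomization weight as baseline unless it was repeated for a deferred start.
4. Report by arm how many never start and how many have no later weight.
5. State whether make-up sessions alone count as receiving a dose of treatment.

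The cost is SAP wording, a few extra contacts, one more analysis and some dilution. With 5% non-starters in each arm losing 0%, the difference is 3.8 points, not 4.0. Power is then about 77%, against about 79% under the current rule if those people are lost on top of the 20% attrition.

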2.4. Role of Physical Activity in Facilitating Long-Term Weight Loss

Physical activity is the most reliable predictor of long-term weight loss.^{9,10} Studies consistently show that participants are more likely to achieve and maintain significant long-term weight loss (e.g., $\geq 10\%$) when they engage in high levels (e.g., $\geq 200-250$ minutes per week) of physical activity.¹⁰⁻¹⁵ For example, in secondary analyses of a randomized controlled trial evaluating the effects of different doses of exercise on weight loss, Jakicic et al showed that participants who reported exercising ≥ 200 min/wk had significantly greater weight loss at month 12 (by 6.3 kg) than participants who exercised <150 min/wk.¹³ Another study found that participants who maintained a 10% weight loss 24 months after treatment reported engaging in an average of 275 min/wk of physical activity.¹² These observational data are supported by findings from some but not all randomized trials.^{12,16}

One pathway to increasing physical activity is by boosting exercise self-efficacy. Self-efficacy – which refers to individuals' confidence in their ability to engage in goal-directed behavior – robustly predicts initiation and maintenance of health behavior change,¹⁷ including weight-loss behaviors such as adherence to diet and physical activity recommendations.¹⁸⁻²⁰ Greater weight-related self-efficacy is associated with greater short- and long-term weight loss²⁰⁻²⁴ and, in comparison to dietary self-efficacy, self-efficacy to exercise is a stronger predictor of weight loss.²⁵ Self-efficacy may naturally decrease during long-term weight-loss maintenance.²³ A recent study found that an intervention designed to increase self-efficacy (combined with standard BWL) resulted in significantly less weight regain from months 12 to 18 of follow-up than BWL alone.²⁶

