Individuals with obesity who experience and internalize weight stigma may benefit from weight loss to improve their health, yet may face stigma-specific barriers to weight loss. In two longitudinal studies, individuals who reported experiencing weight discrimination at baseline were three times more likely to remain obese³⁷ and gained 1.7 more kg than individuals who did not report weight discrimination.³⁸ Recent studies have also illustrated that patients who have experienced and/or internalized weight stigma, in comparison to those who have not, have poorer long-term weight loss outcomes with both behavioral and surgical weight loss interventions.³⁹⁻⁴² For example, in a study of 49 adults with $BMI \geq 27 \text{ kg/m}^2$ who received behavioral weight loss (BWL) treatment, higher frequency of receiving weight-stigmatizing comments from others was associated with less weight loss and less physical activity.³⁹ In another study, participants who consciously or unconsciously endorsed negative weight stereotypes (one aspect of WBI) also lost less weight and reported less physical activity.⁴⁶ Proposed pathways for these effects include a combination of physiological stress responses that increase inflammation and appetite, and maladaptive behavioral coping responses such as increased caloric intake and avoidance of physical activity.³⁴

Acute and long-term studies have shown that weight stigma (particularly WBI) is associated with reduced self-efficacy for dietary control,⁴³ with increased caloric consumption (particularly of unhealthy foods),⁴³⁻⁴⁵ and with worse dietary adherence following bariatric surgery.⁴⁶ In addition, individuals who experience weight stigma feel more self-conscious in fitness settings and are more prone to anticipating future stigmatization in these settings, thus increasing avoidance of physical activity.⁴⁷⁻⁴⁹ In prior work, my colleagues and I have also shown associations between WBI and reduced self-efficacy to engage in physical activity, along with reduced exercise motivation and engagement.⁵⁰ In other words, if individuals with obesity believe that they are lazy and lack willpower (internalized stereotypes), they lose confidence in their ability to follow through on their physical activity goals and are, thus, less likely to engage in their planned physical activity.^{50,51}

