7. STATISTICAL ANALYSIS

Sample size calculation

Using a sample size equation for longitudinal clustered samples,⁸⁴ a power analysis was conducted for the **primary outcome: percent weight change at week 72**. Estimated group means, attrition rate, intraclass correlation (ICC), and variances were derived from data from prior studies

conducted at our Center.⁷² Specifically, we predict a 72-week weight loss of 9% in the stigma + BWL group and 5% in the BWL group, with expected standard deviations of 7%.⁷² Based on these estimates, a baseline sample size of 104 participants (52 per group), assuming a 20% attrition rate, an ICC of .80, and 4 assessment points, will give us 80% power to detect a between-treatment group difference at week 72 of 4% (effect size: 0.57) to be significant at alpha = 0.05. The power analysis was conducted using PASS v14. All secondary outcomes will be considered exploratory and will provide valuable findings that will help to inform larger studies. This study has not been powered to detect differences in changes in physical activity, cardiometabolic outcomes, or psychosocial variables.

Analysis plan

Data quality and integrity will be checked by assessing the data for missing and out-of-range values with basic statistical procedures, including univariate statistics and visual graphical displays (e.g., scatter plots). We will investigate all questions of data quality and integrity prior to performing any statistical modeling. To test the adequacy of randomization, preliminary analyses will include a comparison of all participant demographic and baseline characteristics by randomized treatment groups (t-tests or Wilcoxon rank sum tests for continuous variables and Chi-Square test or Fisher's Exact test for categorical data). If imbalances are observed, the relevant variables will be included as covariates in the final analyses.

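### Baseline covariates enter the mixed model only after a significant chance imbalance and none is fixed in advance, which forgoes precision and leaves the primary model open

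*Combined protocol and SAP*

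**What the plan says.** The Analysis plan in Section 7 builds the primary mixed model from treatment group, time (weeks 20, 46 and 72) and their interaction, with the week 72 contrast as the primary test. No baseline covariate is named.

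Covariates can enter in two ways. The paragraph on data checks compares every demographic and baseline characteristic between the arms by significance test and continues: "If imbalances are observed, the relevant variables will be included as covariates in the final analyses". The paragraph on the mixed model is narrower: "We will include as baseline covariates any variables that differ significantly between the treatment groups at baseline and show significant relationships with the outcome". The general level is given as "Analyses will be two-tailed with a significance level of 0.05".

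The second aim and the secondary aims concern changes in activity, self-efficacy, cardiometabolic risk and psychological measures. These "will be analyzed using the same methods as described above for the mixed effects model used for the primary aim". Under Sample size calculation the plan adds: "All secondary outcomes will be considered exploratory".

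**The concern.** Adjusting for a baseline variable gains precision because the variable predicts the outcome, whether or not it happens to be imbalanced. Both statements make imbalance the gate, and in a randomized trial that gate opens by chance, about one time in twenty per variable at the 0.05 level. A useful predictor is therefore nearly always left out.

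The model is also not settled in advance. The first statement does not define which imbalanced variables are relevant. The second needs a significant relationship with the outcome but does not say at which visit or in which model this is judged, so the primary model cannot be written down until outcome data have been examined. Two analysts could fit different primary models and both claim to follow the plan.

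The stakes are modest: some power for the primary test, wider intervals for secondary outcomes analysed as change, and a primary analysis not fully specified beforehand.

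**Working it through.** **Inputs from Section 7.** 52 per arm; SD 7; difference 4 (effect size 4/7 = 0.57); two-sided 0.05; and "assuming a 20% attrition rate, an ICC of .80, and 4 assessment points".

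**The plan's own figure.** With the time-averaged repeated-measures formula, n per arm = 2 × [SD × (1.96 + 0.8416)/4]² × [1 + (m − 1) × ICC]/m. The first part is 48.07. With m = 4 and ICC 0.80 the second is (1 + 2.4)/4 = 0.85. The product is 40.9, rounded up to 41; 41/0.80 = 51.25, rounded up to 52 per arm, or 104. The stated size reproduces.

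**How often a covariate enters.** Imbalance alone: 5% per variable. Imbalance plus a significant correlation with the week 72 outcome: 0.4%, 2.1%, 3.6% and 5.0% of simulated trials at r = 0, 0.2, 0.3 and 0.5. The number of baseline variables tested is not stated. If it were 10, 20 or 30 independent variables, the chance of at least one significant imbalance would be 1 − 0.95^k = 40%, 64% or 79%, so some adjustment is likely even though any given predictor is rarely chosen.

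**Power of the planned week 72 test.** Simulation of the random-intercept REML model on weeks 20, 46 and 72, with 10 dropouts per arm (20% of 52 is 10.4). Assumed: dropout spread as 3, 3 and 4 before the three visits; one covariate with equal r at each visit, entered with a time interaction. There were 12,000 trials per row, so the standard error of one power figure is √(0.78 × 0.22/12,000), about 0.4 points.

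| r (assumed) | No covariate | Imbalance only | Imbalance and outcome | Always included |
|---|---|---|---|---|
| 0 | 77.6% | 77.4% | 77.6% | 77.2% |
| 0.2 | 78.0% | 78.1% | 78.0% | 79.4% |
| 0.3 | 77.5% | 77.9% | 77.7% | 80.7% |
| 0.5 | 77.8% | 78.8% | 78.8% | 87.4% |

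Forgone power is the last column minus either rule: nothing at r = 0 (inclusion costs up to 0.4), 1.3 to 1.4 at 0.2, 2.8 to 3.0 at 0.3 and 8.6 at 0.5.

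**Cross-check without simulation.** Generalized least squares with known ICC: the outcome covariance has 49 on the diagonal and 0.80 × 49 = 39.2 off it, and a covariate subtracts r² × 49 from every entry. Unadjusted power is 73.5%, 77.7% or 79.7% if dropouts leave before week 20, evenly, or after week 46. At r = 0.3 it becomes 77.4%, 81.2% or 83.1%, a gain of 3.4 to 3.9 points whatever the timing.

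**Type I error.** Under both rules it is 5.0%, 4.6% and 4.2% at r = 0, 0.3 and 0.5 (15,000 trials each). A week 72 analysis of covariance with one or three covariates gives 4.2% to 4.9%. The rules are slightly conservative.

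**Secondary outcomes analysed as change.** The variance with the baseline value included, relative to the change score without it, is (1 − ρ²)/(1 + q² − 2ρq). Here ρ is the baseline to follow-up correlation and q is the baseline SD over the follow-up SD, both assumed.

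| q | ρ = 0.5 | ρ = 0.7 |
|---|---|---|
| 1 | 0.75 | 0.85 |
| 0.8 | 0.89 | 0.98 |
| 0.7 | 0.95 | 1.00 |
| 0.6 | 0.99 | 0.98 |

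The cut is 0% to 25%. Low q is plausible where eligibility truncates the baseline range (Section 5.2: WBIS average of 4 or above; less than 150 minutes of structured activity per week).

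**The case against.** The strongest objection is that the gain may be close to nothing. Section 2.4 says "self-efficacy to exercise is a stronger predictor of weight loss", but the comparison is with dietary self-efficacy, the timing is not given, and the plan treats self-efficacy as something the intervention raises. Section 2.5 says "patients who have experienced and/or internalized weight stigma, in comparison to those who have not, have poorer long-term weight loss outcomes", yet Section 5.2 requires both a stigma history and elevated WBIS, so nobody in this trial belongs to the comparison group. A reader might infer that the plan names proven baseline predictors and then ignores them. The documents suggest that these variables predict weight loss; they do not show it at baseline in this selected sample. That part of the objection stands, and r = 0.5 has no support in the text.

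Second, fixed covariates can cost participants. A standard mixed model drops anyone with a missing covariate. If 5% of baseline scores were missing (assumed) and those participants were dropped, adjusted power at r = 0.2 would be 77.3%, below the unadjusted figure. This is a fair warning, but filling missing baseline values by a simple rule blind to arm removes it.

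Third, the two statements may be one rule, the first being shorthand for the second with 0.05 as the threshold. A reader might call them a contradiction; the text does not support that. It is an ambiguity, and power under the two readings differs by at most 0.2 points.

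Fourth, the primary time factor cannot be carried over literally to cardiometabolic outcomes, which have no week 46 assessment, and the plan does not expressly exclude baseline as a response for other outcomes. So the secondary point holds only for continuous outcomes analysed as change, at the visits where they are measured.

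**Conclusion.** The point holds, as one of precision and of fixing the model in advance. Covariate entry depends on a chance imbalance, a prognostic variable is adjusted for in about 5% of trials or fewer, and no covariate is fixed.

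A reader might infer that choosing covariates by tests on the trial's own data inflates the false-positive rate. Applied mechanically, neither rule does so; the error rate is 4.2% to 5.0%. The discretion left by undefined relevance was not simulated.

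The size is uncertain because r is not in the documents: about 0 to 1.5 power points at r of 0.2 or less, about 3 at 0.3 and about 9 at 0.5, under the stated ICC and attrition and an assumed even dropout. Narrowed WBIS and activity ranges make the low end credible. For the exploratory secondary outcomes, the baseline value does not raise large-sample variance and cuts it by 0% to 25%. The case for change rests on low cost and on settling the model beforehand, not on a demonstrated large loss. The sample size of 104 is not affected.

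**What to change.** Replace both statements with one rule, set before outcome data are examined by arm (the DSMB's own group-level review aside).

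- Name a short covariate list for the primary model from variables already collected. Candidates are the Self-Efficacy for Exercise score, baseline physical activity, screening WBIS and baseline weight. The prior-study data behind the sample size can guide the choice where they contain these variables.
- Enter each covariate with a time interaction, and say so. If r rose from 0 to 0.25 to 0.5 over the visits (assumed), power would be 84.2% with the interaction and 81.0% without.
- Fill missing baseline values by a simple imputation blind to arm, so that no participant is dropped.
- Confirm that baseline questionnaires are completed before allocation is disclosed. Section 6.2 has the accelerometer handed out at the randomization visit and worn afterwards; weigh this before choosing accelerometer activity for the primary list.
- For continuous secondary outcomes analysed as change, include the outcome's own baseline value at the visits where it is measured (weeks 20 and 72 only for cardiometabolic measures).
- Report baseline balance descriptively, and keep imbalance-driven adjustment as a labelled sensitivity analysis.

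The cost is wording; no new data, visits or participants are needed. Each continuous covariate uses three parameters with its time interaction, and one that is not prognostic costs about 0.4 power points (77.6% to 77.2%).
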